Schedule of procedures

Screening, Visit 1

Screening visit. It will include review of inclusion and exclusion criteria and obtaining informed consent from legal guardians and assent from participants. The visit is expected to take around one hour. The visit can be combined with Visit 2.

Participants will be recruited from either an endocrinology inpatient floor or the outpatient clinic.

Baseline, Visit 2

The visit will include review of diabetes history including current doses, prior hospitalizations, previous complications, and detailed medical and social histories and a complete physical examination that will include measurement of height and weight. A capillary blood sample will be obtained for HbA1c determination using the Alere Afinion device. A HbA1c from within two weeks of Visit 2 may also be used. A urine pregnancy test will be performed on females capable of becoming pregnant.

Participants and guardians will be introduced to the concept of a continuous glucose monitor in general, with specific details about how to apply, use, and share the Dexcom G6 data. Mandatory alarms will be set for participants and followers for blood glucose below 70 mg/dL, blood glucoses above 250 mg/dL, “urgent low soon”, “signal loss”, and “no reading” alerts. Participants may set extra alarms to personalize their diabetes alerts. Participants will also be taught to log their food and insulin intake into the CGM device.

Participants will complete the PHQ-9A, PEDS-QoL4, Self-Efficacy for Diabetes Self-Management measure (SEDM) questionnaire, and Collaborative Parent Involvement Scale. A blinded CGM will be placed on the participant with the goal to obtain baseline data for 10 days. A test secure text message will be sent through TigerConnect to guardian and participant, and they will be introduced to the messaging platform used. We will determine with the participants and parents their preferred contact hours and school hours to allow texting for non-urgent matters to be done at convenient times. This visit will take up to 2 hours.

Between Visit 2 and Visit 2T, participants and clinical staff will be notified if there is signal loss from the blinded CGM. Dexcom, Inc. will provide troubleshooting of the blinded CGM if any technical issues arise. Participants will be asked to continue taking care of their diabetes as usual and will not have access to the CGM data.

Telephone or Clinic Follow-up, Visit 2B or 2T

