This will be a telephone call scheduled 10 days (+ 4 days) by a clinical research staff member to review blinded CGM data for the purpose of logging CGM parameters including average glucose with standard deviation, time in range, percent highs, percent lows, and severe lows, and days with CGM data. If the CGM is worn less than 60% of the time, the participant may be withdrawn from the study at the discretion of the study investigator. Each participant, with the help of a guardian, will insert a non-blinded sensor according to the Dexcom G6 user guide, connect the Dexcom to a compatible phone, and activate the share functions with the clinic. If the guardian is not able to set-up the Dexcom at home, the patient and guardian will be asked to come for Visit 2B within 5 days to have the non-blinded Dexcom set-up in clinic and assure that inserting the CGM is a skill that could be done independently. If the guardian or participant cannot demonstrate that they can set-up the CGM system independently, the participant will be withdrawn from the study.

Between Visit 2T and Visit 3, clinic research staff will actively monitor the participants' blood glucose levels remotely through an Apple iPad. Currently available commercial Dexcom software is able to monitor up to 10 devices on a single iPad, and we plan to have two iPads

throughout the study period. Active remote monitoring of CGM data will occur during 7 days per week between 8:00 AM and 8:00 PM.

The goal of the secure text messaging is to provide supervision and feedback to the adolescents that is supportive and collaborative, with the ultimate goals of increasing self-efficacy and improving diabetic self-management skills. The intention is not to make the texting platform cumbersome and to allow the participants freedom in making lifestyle choices that will not interfere with their diabetes control. Only reactive texts and coaching texts will be sent during the school hours.

Participants will still be able to use normal clinic communication methods through the electronic patient portal and diabetes telephone emergency line as usual. Participants will be free to optimize their treatment independently as previously educated about trend management. We will provide a letter for school indicating that the participants are a part of a study and they have to carry their cell phones with them and respond to text messaging from us.

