Reminder texts will also be sent to remind participants and guardians about upcoming research Visit appointments.

- Reinforcing. Texts will provide encouragement and reinforcement for adherence to diabetes related tasks. Examples will include texts stating “(screenshot image from the participant’s glucose trend), followed by “awesome control! Keep it up!”.
- Coaching. Texts in this category will include response to participants and guardians’ complaints and questions. They could include management of participant or guardian questions about abnormal blood glucoses or ketone management interventions. Clinic protocols to manage sick days will be utilized.

All Tigertext communication will be stored electronically in a secure shared file. It will be used to retrospectively calculate time invested by clinical staff, and analyze percentage of texting category used.

First Follow-up, Visit 3

This visit will be scheduled 11-12 weeks (+/- 5 days) after Visit 2B or visit 2T. Adverse events, insulin doses and concomitant medications will be reviewed by study staff. Height and weight will be measured, and a physical exam will be performed. A capillary blood sample will be obtained for HbA1c determination. CGM reports will be analyzed. Participants will complete the PHQ-9A, PEDS-QoL4, Collaborative Parent Involvement Scale, and SEDM.

If due to participant or family scheduling conflicts, the participant is unable to complete a clinic visit for Visit 3, then they can participate in a telemedicine visit. Participants will be requested to measure height and weight at home. A physical exam will be performed as fully able within the telemedicine platform. HbA1c will be obtained with other standard of care labs. CGM report analysis will not be affected by the telemedicine visit. Surveys for PHQ-9A, PEDS-QoL4, Collaborative Parent Involvement Scale, and SEDM will be sent via MyChart to the participant’s parent to be completed by the participant. Parents will send images of the completed surveys to the research team via MyChart.

We will discuss the next phase of the study during that visit. We will emphasize that the research staff will not monitor CGM data remotely, that research staff will not be real-time followers of their CGM data, and they will not be able to use TigerText to communicate with our clinic anymore. They will be encouraged to continue the activated alarms to allow for self-control.

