We will discuss that CGMs will continue to be made available to participants and guardians for diabetes care. Participants and guardians will still be able to communicate with our clinic through previously available means, mainly through the electronic participant portal and/or calling the urgent line, and they could ask the clinic staff to review past CGM readings to give clinical advice.

Second Follow-up, Visit 4/EOSV

This visit will be scheduled 11-12 weeks (+/- 5 days) after Visit 3. Adverse events, insulin doses and concomitant medications will be reviewed by study staff. Height and weight will be measured, and a physical exam will be performed. A capillary blood sample will be obtained for HbA1c. Participants will complete the PHQ-9A and PEDS-QoL4 surveys, Collaborative Parent Involvement Scale, and SEDM.

If due to participant or family scheduling conflicts, the participant is unable to complete a clinic visit for Visit 4, then they can participate in a telemedicine visit. Participants will be requested to measure height and weight at home. A physical exam will be performed as fully able within the telemedicine platform. HbA1c will be obtained with other standard of care labs. CGM report analysis will not be affected by the telemedicine visit. Surveys for PHQ-9A, PEDS-QoL4, Collaborative Parent Involvement Scale, and SEDM will be sent via MyChart to the participant's parent to be completed by the participant. Parents will send images of the completed surveys to the research team via MyChart.

This is the final study visit.

Evaluations

Medical History

- Age
- Gender
- Race/ethnicity
- Date of diagnosis of type 1 diabetes
- Hospitalizations and emergency department visits, particularly for diabetic ketoacidosis or hyperglycemia/ketosis/vomiting, or for severe hypoglycemia
- Surgeries
- Growth records for both height and weight
- Current doses of insulin
- Meal plan
- Other chronic medical conditions, particularly hypothyroidism or celiac disease
- Concomitant medications

Social history

- Family structure—one or two parent household, parents married or divorced, custody arrangements if divorced, genders and ages of siblings

- School details: name, grade, extracurricular activities, sports, schedule, school nurse information, and information about student insulin dosing during school hours if it is done through school nurse or independently by student.

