Collaborative Parent Involvement Scale		X		X	X

[figure not shown]

Figure 1. Timeline for study. Study visits are denoted by arrows. A timescale in months is below the timeline; there is not a specified interval between Visits 1 & 2.

Participant withdrawal criteria

The following study withdrawal criteria will apply:

1. Participants can terminate involvement in the study at any time point without any repercussions.
2. If data on the CGM is available < 60% of the time worn, patient may be withdrawn at the discretion of the research investigator.
3. If pregnancy occurs during study period.
4. Allergic reaction to adhesive surface of CGM sensor

Primary endpoint

The primary outcome is change in Hemoglobin A1c (HbA1c) between the baseline visit (Visit 2) and three-month follow-up visit (Visit 3) after active remote monitoring and secure text messaging.

A 5% significance level will be used to declare statistical significance for the primary outcome comparison.

Exploratory endpoints

- Change in Peds PHQ-9A, PED-QOL4A, SEDM, and Collaborative Parent Involvement Scale scores.
- Time taken for a text to be read by participant and guardian.
- Time spent by medical provider per participant per day.
- The difference in A1c between clinical remote monitoring HbA1c (Visit 3) and self-monitoring utilizing CGM (Visit 4)
- The difference in A1c from baseline (Visit 2) and after the two phases of the study intervention (Visit 4).
- The following outcomes will be compared between baseline, three months and six months using repeated measures ANOVA as follows:
 - Time spent in the target glucose range from 70–180 mg/dL
 - Time spent below target glucose 70 mg/dL

- Time spent above target glucose 180 mg/dL
- Average of time the participants wore the CGM

Statistical Plan

Paired sample t-tests will be used to assess continuous variable differences between two time points. Generalized linear models will be run to identify items in medical and social histories that could predict hemoglobin A1c, the primary outcome. Point estimates will be reported with 95% CIs.

As this is a pilot exploratory study, we will implement per-protocol analysis and not an intention-to-treat analysis. Only patients who have completed the three phases of the study will be included for analysis.

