Utilizing a standard deviation of HbA1c of 1.5%, a sample size of 18 participants will be required to detect a 1% change in HbA1c between the baseline measurement and 3-month measurement, assuming an alpha of 0.05 and a beta of 0.20 (80% power).

Safety endpoints

The following safety outcomes will be tabulated by treatment group:

- Number of subjects with any DKA events requiring hospitalization
- Number of subjects with any severe hypoglycemic or hyperglycemic events requiring an emergency room visit or hospitalization
- Number of episodes of moderate to large ketones managed in an outpatient basis

All adverse events will be listed for the entire study duration.

Data management

Dexcom Clarity reports will be used to obtain aggregate 90-day data regarding CGM parameters including average glucose with standard deviation, time in range, percent highs, percent lows, severe lows, and percent days with CGM data (this will be used to compare data across Visits 2T and Visit 4). Additionally, we will collect above data points retrospectively week-by-week for secondary analysis to evaluate progress over time.

Confidentiality of participant data will be observed during the study. Electronic data will be stored in secure password protected computers, and all paper records will be stored in locked researcher's offices. Anonymous data could be shared with third parties to advance diabetes treatment and for study publication purposes.

Protections Against Risk

Confidentiality

Privacy of Personal Data

The collection and processing of personal data from subjects enrolled in this study will be limited to those data that are necessary to fulfill the objectives of the study. These data will be collected and processed with adequate precautions to ensure confidentiality and compliance with applicable data privacy protection laws and regulations. Electronic data will be stored on secure servers that require password protection and maintain audit records of access, and/or on laptops with password-protected encrypted hard drives. All data sent between institutions via e-mail, file transfer protocols or physical media must be encrypted and password protected. Sponsor personnel whose responsibilities require access to personal data agree to keep the identity of study subjects confidential. Hardcopy documentation must be stored in locked file cabinets or locked offices secured with either key or badge access.

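### The 90-day CGM aggregates are longer than any study phase: the Visit 4 value takes in remotely monitored days, and no 90-day value can exist at Visit 2T

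*Combined protocol and SAP*

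**What the plan says.** The section Data management sets the rule: "Dexcom Clarity reports will be used to obtain aggregate 90-day data regarding CGM parameters". The parameters include mean glucose, the time-in-range measures and percent days with data. A parenthesis gives the purpose: "this will be used to compare data across Visits 2T and Visit 4". The same section plans week-by-week retrieval of these parameters, but assigns it to a secondary look at progress over time.

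Four other places fix the calendar:

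- Baseline, Visit 2: "A blinded CGM will be placed on the participant with the goal to obtain baseline data for 10 days".
- Telephone or Clinic Follow-up, Visit 2B or 2T: "This will be a telephone call scheduled 10 days (+ 4 days) by a clinical research staff member". If home set-up of the unblinded sensor fails, "the patient and guardian will be asked to come for Visit 2B within 5 days".
- First Follow-up, Visit 3: "This visit will be scheduled 11-12 weeks (+/- 5 days) after Visit 2B or visit 2T".
- Second Follow-up, Visit 4/EOSV: "This visit will be scheduled 11-12 weeks (+/- 5 days) after Visit 3".

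Exploratory endpoints then lists time in, below and above range, and wear time, with this instruction: "The following outcomes will be compared between baseline, three months and six months using repeated measures ANOVA as follows". It gives no data window for any of the three time points.

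**The concern.** Each phase is a different condition: blinded sensor, unblinded sensor with clinic monitoring, unblinded sensor without it. A CGM summary is interpretable only if its days come from one condition. A 90-day report is longer than the schedule allows any phase to be, so followed literally it mixes conditions.

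The mixing matters most at Visit 4. The Overview of methodology describes the third phase as exploring whether improvement persists once monitoring is withdrawn. Monitored days inside the Visit 4 value bear directly on that question. At Visit 2T the problem is different: the study has not yet generated 90 days of data, so the rule cannot be applied at one end of the comparison it is meant to serve.

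**Working it through.** **Inputs.** Window of 90 days (Data management). Phases 2 and 3 each 11 or 12 weeks, plus or minus 5 days (Visit 3 and Visit 4 sections). Blinded session of 10 days (Visit 2 section). Visit 2T at day 10 to 14, with Visit 2B up to 5 days later (Visit 2B/2T section).

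**Assumption.** The plan does not say where the 90-day window sits. I take it to end at the visit.

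**Can the plan's 90 days be reproduced from the schedule?** Phase length = 7 × weeks ± 5. Overrun = 90 − phase length. Share = overrun / 90.

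| Timing | Phase length (days) | Overrun (days) | Share of window |
|---|---|---|---|
| 11 weeks − 5 days | 72 | 18 | 20.0% |
| 11 weeks | 77 | 13 | 14.4% |
| 11 weeks + 5 days | 82 | 8 | 8.9% |
| 12 weeks − 5 days | 79 | 11 | 12.2% |
| 12 weeks | 84 | 6 | 6.7% |
| 12 weeks + 5 days | 89 | 1 | 1.1% |

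It cannot. The longest permitted phase is 89 days, so 90 elapsed days do not fit inside a phase wherever the window is placed. At 89 days, counting both end dates, the overrun is only the transition day.

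**Visit 4.** The overrun days all belong to phase 2, because two phases span at least 2 × 72 = 144 days. No sensor gap is planned between phases 2 and 3. Let B, P2 and P3 be the true means in the three phases and f the share in the table, with equal wear throughout. The 90-day value at Visit 4 is (1 − f)P3 + fP2. Its difference from a clean baseline is

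(P3 − B) + f(P2 − P3).

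If control returned fully to baseline in phase 3 (P3 = B), the report would still show f(P2 − B): 7% to 14% of the phase 2 gain at nominal timing, and up to 20% at the earliest permitted visit. These are calendar shares. If wear were lower in phase 3 than late in phase 2, the monitored days would make up a larger share of the readings.

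**Visit 3.** The calendar overrun is the same, but the content differs. The blinded session holds about 10 days, so an 18-day reach-back cannot yield 18 days of blinded data. At the 72-day extreme, 10 blinded days are 10/(72 + 10) = 12% of available days; if recording ran to day 14, 14/(72 + 14) = 16%. A Visit 2B gap of up to 5 days would leave 6 − 5 = 1 day of a 6-day reach-back. If blinded data are held in a separate report, the overlap is nil.

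**Visit 2T.** Study data available: 10/90 = 11% of the nominal window, or 14/90 = 16% at most. If percent days with data used 90 as its denominator, a participant with perfect wear would score 11% to 16%.

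**Direction of bias between Visits 3 and 4.** Let g be the blinded share in the Visit 3 window. Then

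Visit 4 − Visit 3 = (1 − f)(P3 − P2) + g(P2 − B).

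With g = 0 this is simple attenuation by f. With g > 0 it is not: if P3 = P2, a difference of g(P2 − B) appears where none exists.

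**The case against.** The strongest reply is that the protocol already defines baseline as the blinded session, reviewed at Visit 2T. On that view 90-day is loose shorthand for a roughly three-month phase, and the weekly retrieval means nothing is lost. Much of this stands: nobody reading the whole protocol would think a 90-day baseline was intended, and the weekly data make repair easy. But the 90-day rule is the only stated definition for the main CGM summary, and the weekly data are assigned elsewhere. An analyst who follows the text obtains a contaminated Visit 4 value.

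A second reply is that naming Visits 2T and 4 may mean spanning them. The schedule table has CGM data reviewed at Visits 2T, 3 and 4, and the endpoint list compares three times. That is a fair reading, so I treat this as wording to clarify rather than a separate fault.

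Four stronger conclusions are tempting and not supported:

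- *Every window is contaminated.* This is shown for Visit 4. For Visit 3 it depends on whether blinded data enter the same report, which is not stated.
- *All phase contrasts are diluted by 1% to 20% toward no change.* The expressions above show that size and direction depend on which windows are contaminated and on the true phase means.
- *A fall in wear time from baseline is guaranteed by the 60% rule.* Withdrawal under that rule is at the investigator's discretion, and the withdrawal criteria do not confine it to the run-in. Unblinding, and the phase 2 text sent after 4 hours without data, could raise wear. Regression to the mean is possible; a fall is not built in.
- *Repeated measures ANOVA must be replaced.* The Statistical Plan already limits analysis to those who completed all three phases, so the ANOVA itself is not what removes dropouts. On this point a change of model is a preference.

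**Conclusion.** The concern holds for Visit 4 and Visit 2T, and conditionally for Visit 3. A 90-day report ending at Visit 4 mixes 1 to 18 monitored days into the estimate for the unmonitored phase, 6 to 13 of them at nominal timing. No 90-day study value can exist at Visit 2T.

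The Visit 4 figures rest on a window that ends at the visit and on visits kept within their permitted ranges. The conclusion that 90 elapsed days cannot fit inside a phase needs only the second.

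The consequence is modest. These are exploratory outcomes in an uncontrolled pilot of 25, and the HbA1c endpoints do not depend on the CGM window. It is still worth correcting, because the affected contrast addresses the stated purpose of phase 3 and the correction costs almost nothing. Change in wear from baseline should be read with caution, because baseline wear is subject to a discretionary selection rule.

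**What to change.** In Data management, replace the 90-day rule with windows bounded by phase:

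- **Baseline:** the blinded session only.
- **Phase 2:** first full day after unblinded set-up (Visit 2T or 2B) to the day before Visit 3.
- **Phase 3:** first full day after Visit 3 to the day before Visit 4.

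Use the number of days in each window as the denominator for percent days with data. State that all three time points in Exploratory endpoints are compared. Make the whole-phase summaries the main analysis, and add the last 10 days of each phase as a sensitivity comparison of equal length with baseline. Count the planned weekly blocks from the start of each phase, so that none straddles Visit 3. Add a sentence that baseline wear is subject to the discretionary 60% rule.

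The cost is a few lines of wording and different date ranges in reports the study already draws. The planned weekly retrieval implies that date ranges can be set. No new visits or measurements are needed.
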